7.2.2.3. Complete TMA Response Status Over Time and Alternative Definitions

Complete TMA Response will also be summarized over time by presenting the number and proportion of responders along with a 2-sided 95% CI for each postbaseline time point. This summary will be accompanied by a similar presentation for the components of complete TMA response: proportion of patients with platelet count normalization, proportion of patients with LDH normalization, proportion of patients with hematologic normalization (platelet count and LDH), proportion of patients with $\geq 25\%$ improvement in serum creatinine from baseline. The CIs will be based on the asymptotic Gaussian approximation method with a continuity correction. These tabular summaries will be accompanied by a bar chart graphical figure displaying for each time point a bar for Complete TMA Response and each component in its definition, where the bar will represent the proportion of patients meeting that specific criterion.

A patient will be included in the analysis for a specific postbaseline time point if it was possible for the result at that time point to be confirmed or to serve as a confirmatory result.

A set of summaries similar to the ones described above will be produced without any requirement for a confirmatory result. This summary will be strictly based on a patient meeting the criterion at a specific time point.

A slightly modified version of complete TMA response will also be evaluated. The modification will only affect patients considered to be on dialysis at baseline (ie. patients requiring dialysis within 5 days prior to ALXN1210 treatment initiation). For these patients, the criterion requiring

an improvement from baseline of 25% or more in serum creatinine, will be replaced by a postbaseline change in dialysis status (from requiring dialysis at baseline to no longer requiring dialysis) that is maintained for at least 4 weeks. A set of summaries similar to the ones described above will be produced based on this alternative definition.

The tabular summary of complete TMA response over time will also be performed on the PPS.

7.2.2.4. eGFR Value and Change from Baseline

Kidney function evaluated by eGFR will be summarized at baseline and each postbaseline time point using descriptive statistics for continuous variables for the observed value as well as the change from baseline. A value for eGFR will be imputed for patients requiring dialysis for acute kidney injury (see [Section 9.4.9](#) for details). This summary will be repeated by the kidney transplant status at enrollment, and on the PPS

A mixed model for repeated measures (MMRM) will be used to improve the precision of estimation of changes in eGFR over time. The model will include the fixed, categorical effect of visit and fixed, continuous effect of the baseline value as covariates. An unstructured covariance structure will be used to model the within patient errors. If this analysis fails to converge, the following structures will be tested and the final covariance structure will be determined by selecting the one with the lowest Akaike's information criterion (AIC): first-order autoregressive, compound symmetry, and Toeplitz. The Kenward-Roger approximation will be used to estimate denominator degrees of freedom. The estimation of change from baseline on defined weeks alongside with 95% confidence intervals will be provided.

Figures presenting the observed values and the model based values over time will be provided.

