7.1. Summary of Study Design

Study ALXN1210-aHUS-311 is a Phase 3, open-label, single arm, multicenter study to evaluate the safety and efficacy of ALXN1210 administered by intravenous (IV) infusion to adolescent (12 to < 18 years of age) and adult (≥ 18 years of age) patients with aHUS. The study will enroll approximately 55 patients to receive ALXN1210. All patients must be naïve to complement inhibitor treatment and include at least 6 and up to 10 adolescent (12 to < 18 years of age at Screening) patients and at least 10 and up to 25 patients with prior kidney transplants. A minimum of 30 patients who meet all laboratory criteria for TMA (platelet count of < 150,000 per microliter, LDH $\geq 1.5 \times$ upper limit of normal (ULN), hemoglobin \leq lower limit of normal (LLN), and serum creatinine level \geq ULN) as determined by the central laboratory at Day 1, will be enrolled.

The study consists of an up to 7 day Screening Period, a 26-week Initial Evaluation Period, and an Extension Period until the product is registered or approved (in accordance with country-specific regulations) or for up to 4.5 years, whichever occurs first. Dosages are based on the patient's body weight recorded at the last visit or more recently (Table 6). Patients will receive a loading dose of ALXN1210 IV (2400 mg for patients weighing ≥ 40 to < 60 kg, 2700 mg for patients weighing ≥ 60 to < 100 kg, 3000 mg for patients weighing ≥ 100 kg) on Day 1, followed by maintenance doses of ALXN1210 IV (3000 mg for patients weighing ≥ 40 to < 60 kg, 3300 mg for patients weighing ≥ 60 to < 100 kg, 3600 mg for patients weighing ≥ 100 kg) on Day 15 and once every 8 weeks (q8w) thereafter for a total of 26 weeks of treatment in the Initial Evaluation Period followed by maintenance doses q8w in the Extension Period (Figure 1). The end of trial is defined as the last patient's last visit.

Figure 1 illustrates the study design.

Figure 1: Study Design Schematic for Clinical Protocol ALXN1210-aHUS-311

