8.1. Inclusion Criteria

Patients are eligible for enrollment in the study only if they meet all of the following criteria and none of the exclusion criteria:

1. Male or female patients ≥ 12 years of age and weighing ≥ 40 kg at the time of consent.
2. Evidence of TMA, including thrombocytopenia, evidence of hemolysis, and kidney injury, based on the following laboratory findings:
 - a. Platelet count < 150,000 per microliter (μL) during the Screening Period or within 28 days prior to the start of the Screening Period, **and**
 - b. LDH $\geq 1.5 \times$ upper limit of normal (ULN) during the Screening Period or within 28 days prior to the start of the Screening Period, and hemoglobin \leq lower limit of normal (LLN) for age and gender during the Screening Period or within 28 days prior to the start of the Screening Period, **and**
 - c. Serum creatinine level \geq ULN during the Screening Period in adults (≥ 18 years of age), or $\geq 97.5^{\text{th}}$ percentile for age ([Appendix A](#)) at Screening in adolescents (12 to < 18 years of age) (patients who require dialysis for acute kidney injury are also eligible).
3. Among patients with a kidney transplant:
 - a. Known history of aHUS prior to current kidney transplant, **or**
 - b. No known history of aHUS, and persistent evidence of TMA at least 4 days after modifying the immunosuppressive regimen (eg, suspending or reducing the dose) of calcineurin inhibitor ([CNI]; eg, cyclosporine, tacrolimus) or mammalian target of rapamycin inhibitor ([mTORi]; eg, sirolimus, everolimus).
4. Among patients with onset of TMA postpartum, persistent evidence of TMA for > 3 days after the day of childbirth.
5. To reduce the risk of meningococcal infection (*Neisseria meningitidis*), all patients must be vaccinated against meningococcal infections within 3 years prior to, or at the time of,

initiating study drug. Patients who receive a meningococcal vaccine less than 2 weeks before initiating ALXN1210 treatment must receive treatment with appropriate prophylactic antibiotics until 2 weeks after vaccination. Patients who have not been vaccinated prior to initiating ALXN1210 treatment should receive prophylactic antibiotics prior to and for at least 2 weeks after meningococcal vaccination.

6. Patients < 18 years of age must have been vaccinated against *Haemophilus influenzae* type b (Hib) and *Streptococcus pneumoniae* according to national and local vaccination schedule guidelines.

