12. Identified drug exposure-related HUS.
13. Receiving PE/PI, for 28 days or longer, prior to the start of Screening for the current TMA.
14. History of malignancy within 5 years of Screening with the exception of a nonmelanoma skin cancer or carcinoma in situ of the cervix that has been treated with no evidence of recurrence.
15. Bone marrow transplant (BMT)/hematopoietic stem cell transplant (HSCT) within the last 6 months prior to the start of Screening.
16. HUS related to known genetic defects of cobalamin C metabolism.
17. Known systemic sclerosis (scleroderma), systemic lupus erythematosus (SLE), or antiphospholipid antibody positivity or syndrome.
18. Chronic dialysis (defined as dialysis on a regular basis as renal replacement therapy for ESKD).
19. Patients receiving chronic intravenous immunoglobulin (IVIg) within 8 weeks prior the start of Screening, unless for unrelated medical condition (eg, hypogammaglobinemia); or chronic rituximab therapy within 12 weeks prior to the start of Screening.

20. Patients receiving other immunosuppressive therapies such as steroids, mTORi (eg, sirolimus, everolimus), CNI (eg, cyclosporine or tacrolimus) are excluded unless:
 - a. part of an established post-transplant antirejection regimen, or
 - b. patient has confirmed anti-complement factor antibodies requiring immunosuppressive therapy, or
 - c. steroids are being used for a condition other than aHUS (eg, asthma).
21. Participation in another interventional treatment study or use of any experimental therapy within 30 days before initiation of study drug on Day 1 in this study or within 5 half-lives of that investigational product, whichever is greater.
22. Prior use of eculizumab or other complement inhibitors.
23. Hypersensitivity to any ingredient contained in the study drug, including hypersensitivity to murine proteins.
24. Any medical or psychological condition that, in the opinion of the Investigator or Sponsor, could increase the risk to the patient by participating in the study or confound the outcome of the study.
25. Known or suspected history of drug or alcohol abuse or dependence within 1 year prior to the start of Screening.
26. Use of tranexamic acid within 7 days prior to Screening is prohibited.

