5. DEFINITIONS

5.1. Efficacy

5.1.1. Primary Endpoint(s)

The primary efficacy endpoint of the study is Complete TMA Response during the 26 week Initial Evaluation Period. The criteria for Complete TMA Response are the following:

1. Normalization of platelet count (defined as platelet count $\geq 150,000$ per microliter)
2. Normalization of LDH (defined as LDH \leq upper limit of normal)
3. $\geq 25\%$ improvement in serum creatinine from baseline

Patients must meet all Complete TMA Response criteria at 2 separate assessments obtained at least 4 weeks (28 days) apart, and any measurement in between.

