7.2.1.2. Subgroup Analysis

The primary efficacy analysis will be repeated separately by the following subgroups:

- gender (male, female)
- race
- ethnicity
- geographic region (by country)
- age at enrollment categories (12-17, 18 years of age and up)
- kidney transplant history (yes, no)
- immunogenicity status (ever positive, always negative)
- dialysis within 5 days prior to treatment initiation (yes, no)
- met all laboratory criteria for TMA as determined by the central laboratory at Day 1

Given that the number of patients in these subgroups may be limited, the CIs will be based on exact confidence limits using the Clopper-Pearson method. For the same reason, some subgroup categories may be combined.

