7.2.2.5. CKD Stage

CKD stage will be summarized over time by presenting the number and proportion of patients that improved (excluding those with Stage 1 at baseline as they cannot improve), worsened (excluding those with Stage 5 at baseline as they cannot worsen), and stayed the same compared to CKD stage at baseline. Stage 5 will be considered the worst category, while stage 1 will be considered the best category (see [Section 9.4.11](#) for details). A 2-sided 95% CI for each proportion will be provided. The CIs will be based on exact confidence limits using the Clopper-Pearson method. This summary will be repeated by the kidney transplant status at enrollment.

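### Platelet, LDH and hematologic normalization rates in SAP 7.2.2.3 include patients who may already be normal at first dose, so they can overstate normalization on treatment by an unknown amount

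*SAP*

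**What the plan says.** **Entry.** Protocol 8.1, criterion 2a, accepts "Platelet count < 150,000 per microliter (μL) during the Screening Period or within 28 days prior to the start of the Screening Period". Criterion 2b sets the same window for LDH and hemoglobin: "during the Screening Period or within 28 days prior to the start of the Screening Period". Protocol 8.1 and SAP 5.2.3 allow local results for both. Only the creatinine criterion (2c) is tied to Screening itself, and it is the only laboratory part of criterion 2 that SAP 6.1 requires for the FAS.

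**Expected mix at Day 1.** Protocol 7.1 plans about 55 patients and commits to "A minimum of 30 patients who meet all laboratory criteria for TMA" by central laboratory at Day 1. The criteria are four: platelets, LDH, hemoglobin and creatinine.

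**Definition.** SAP 5.1.1 lists "Normalization of platelet count (defined as platelet count" of at least 150,000 per microliter), and LDH at or below ULN. Both are thresholds on the value at the assessment. Neither requires an abnormal starting value.

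**Component summaries.** SAP 7.2.2.3 gives the "proportion of patients with platelet count normalization, proportion of patients with LDH normalization, proportion of patients with hematologic normalization (platelet count and LDH") at each postbaseline visit, with a bar chart, once with confirmation and once without. In the confirmed version, inclusion at a visit depends on whether the result could be confirmed or could confirm another. Baseline status plays no part in either version.

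**Existing subgroup.** SAP 7.2.1.2 includes patients who "met all laboratory criteria for TMA as determined by the central laboratory at Day 1", but that section repeats only the primary efficacy analysis.

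**The concern.** The word normalization suggests a move from abnormal to normal, but the tables count a state. A patient can qualify on an old low platelet count and high LDH, recover before Day 1, and be counted as normalized from the first visit. Recovery before first dose is plausible within the plan. The qualifying values may be weeks old, and plasma therapy before Screening is excluded only in the case "Receiving PE/PI, for 28 days or longer, prior to the start of Screening for the current TMA", so shorter courses are allowed.

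The trial has a single arm, and Protocol 7.2 and SAP 7.2.1 say that results will be read in the context of eculizumab studies. A reader of the component tables will want to know how often abnormal platelets and LDH became normal on ALXN1210. If some patients started normal, the planned rates mix that with recovery before the first dose, and no planned table separates the two.

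**Working it through.** **1. Age of the qualifying value.** 28 days before Screening plus a Screening Period of up to 7 days gives about 35 days before first dose.

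**2. The plan's own precision figure (SAP 9.3).** At 65% and n = 50, the continuity-corrected half-width is 1.96 × √(0.65 × 0.35 / 50) + 1/(2 × 50) = 0.132 + 0.010 = 14.2 points, in line with the stated approximately 15%. This figure is not in dispute; the same formula prices the fix below. The plan states no expected normalization rate.

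**3. Effect on a component rate.** Let N = 55, k = patients already normal at first dose, r = rate among patients abnormal at first dose, and s = share of the already-normal who are normal at the visit. Then

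reported rate = [s·k + r·(N − k)] / N, so reported rate − r = k·(s − r) / N.

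The reported rate exceeds r only if k > 0 and s > r. The documents give none of k, r or s, so the values below are assumptions.

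| r | s | k = 0 | k = 5 | k = 10 |
|---|---|---|---|---|
| 65% | 1.0 | 0 | +3.2 (68.2%) | +6.4 (71.4%) |
| 65% | 0.9 | 0 | +2.3 (67.3%) | +4.5 (69.5%) |
| 80% | 1.0 | 0 | +1.8 (81.8%) | +3.6 (83.6%) |
| 80% | 0.9 | 0 | +0.9 (80.9%) | +1.8 (81.8%) |

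Example: r = 65%, s = 1, k = 5 gives (5 + 0.65 × 50)/55 = 37.5/55 = 68.2%.

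The 65% is borrowed from the plan's assumption for the composite. A component is met whenever the composite is met, so its rate cannot be lower than the composite rate, and 65% is towards the low end for a component. An r of 50% is left out: with k = 5 and s = 1 it gives 54.5%, below the 65% that the plan assumes for the composite.

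**4. What the other planned outputs give.**
- SAP 7.3.3.1, shift tables: baseline against postbaseline category for each test, by visit. They show how many started normal, but on the Safety Set, by normal range, one test at a time, and without confirmation.
- SAP 7.2.2.6: observed values, change from baseline and a baseline-adjusted MMRM for platelets and LDH. These are summaries of level and change, not rates.
- SAP 7.2.2, by-patient listings: the raw material, but no rates.
- SAP 6.2, PPS: requires criterion 2, which carries the same 28-day window.
- SAP 7.2.1.2, Day 1 subgroup: the primary proportion only.

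None gives platelet, LDH or joint normalization rates among FAS patients who were abnormal at baseline.

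**The case against.** The case for leaving the tables alone has force. Component normalization is not a listed endpoint: SAP 5.1.2 lists observed values and change from baseline in platelets, LDH and hemoglobin, plus confirmed hemoglobin increase. The component rates accompany Complete TMA Response to show which criterion is met, and reporting a state in the same patients as the composite is legitimate. Nothing is tested (SAP 7.2.1.4). The shift tables and change-from-baseline summaries already show part of the baseline mix. Because plasma therapy is prohibited after the first dose (Protocol 9.7), staying normal may itself partly reflect the drug. All of this stands. It limits the point to a supplement; it does not supply the missing rates.

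A reader might also take the CKD rule in SAP 7.2.2.5, "excluding those with Stage 1 at baseline as they cannot improve", as proof that 7.2.2.3 repeats an error the SAP avoids elsewhere. The parallel is useful but not exact. CKD improvement is defined as change, so patients who cannot change must be left out; the component tables describe a state, where the all-patient rate is valid but incomplete.

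A reader might infer that the comparison with eculizumab is biased. How those studies counted normalization is not in the documents, so this cannot be shown.

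**Conclusion.** The mechanism holds on the text: the planned component rates count patients who were already normal and stayed so, and can therefore overstate normalization on treatment. Whether they do, and by how much, is unknown. The effect is zero if k = 0; with r = 65% and s = 1 it is about 3 points at k = 5 and 6 at k = 10, and it shrinks as r rises or s falls.

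Two stronger readings are not supported.

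- From 55 − 30 = 25, a reader might infer that 45% of patients could enter already normal and that the rates could be some 16 points too high (25 × 0.35/55). But 25 is a ceiling on missing any one of four criteria. A patient can miss on hemoglobin alone, on creatinine, or with LDH above ULN but below 1.5 × ULN, and be normal on neither platelets nor LDH. Thirty is also a minimum, not a forecast.
- A reader might infer that the primary result is inflated in the same way. Complete TMA Response also needs at least 25% improvement in creatinine, so an already-normal patient is not automatically a responder, and the Day 1 subgroup already addresses this for the primary proportion.

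This is an inexpensive improvement to descriptive secondary tables, worth making because it changes what those rates can show in a single-arm trial.

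**What to change.** In SAP 7.2.2.3, keep the FAS rates and add:

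1. The number of patients already normal at baseline on platelets, on LDH, and on both.
2. Platelet, LDH and hematologic normalization rates by visit among patients abnormal predose on the relevant parameter, with a stated rule for the joint measure.
3. A statement of whether abnormal is judged on the last central predose value or on the averaged baseline of SAP 9.4.2. The two can disagree for a patient who recovers between Screening and Day 1.
4. The component tables repeated for the Day 1 all-criteria subgroup of SAP 7.2.1.2, in which no patient is already normal on platelets or LDH at Day 1.

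The primary endpoint, the FAS and data collection do not change. A subgroup by plasma exchange or infusion before first dose is optional and not part of this correction.

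The cost is SAP wording and a few tables, with smaller denominators and wider intervals. For a 65% rate, the continuity-corrected half-width is 0.126 + 1/110 = 13.5 points at n = 55, against 0.171 + 1/60 = 18.7 points at n = 30.

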8. STUDY POPULATION

A total of approximately 55 patients with documented aHUS will be enrolled and assigned to treatment with ALXN1210 at approximately 200 investigative sites globally. The study will enroll at least 6 and up to 10 adolescent (12 to < 18 years of age at Screening) patients and at least 10 and up to 25 patients with prior kidney transplants. A minimum of 30 patients who meet all laboratory criteria for TMA (platelet count of < 150,000 per microliter, LDH $\geq 1.5 \times$ upper limit of normal (ULN), hemoglobin \leq lower limit of normal (LLN), and serum creatinine level \geq ULN) as determined by the central laboratory at Day 1, will be enrolled.

Individuals who do not satisfy the criteria for participation in this study (screen failure) may be rescreened based on discussion and agreement between the Investigator and the Medical Monitor. Patients may be rescreened a maximum of 2 times.

Prospective approval of protocol deviations to recruitment and enrollment criteria, also known as protocol waivers or exemptions, is not permitted.

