7.2.2.1. Dialysis Requirement Status

An analysis will present the number and proportion of patients that are requiring dialysis over time. A 2-sided 95% CI for the proportion will be provided. The CI will be based on exact confidence limits using the Clopper-Pearson method. The summary will be produced for patients requiring dialysis within 5 days prior to ALXN1210 treatment initiation, not requiring dialysis within 5 days prior to ALXN1210 treatment initiation, and overall. A patient will be considered as not requiring dialysis at a specific postbaseline time point if they have been dialysis free for at least 5 days prior to that time point. A by-patient figure showing dialysis status or events over time will be presented.

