9.3. Sample Size, Power, and Randomization

Approximately 55 patients will be enrolled in this study in order to yield at least 50 evaluable patients by Day 183. This sample size is deemed appropriate to provide complete safety information and the necessary precision level for the planned estimation. Assuming a proportion of Complete TMA response of 65%, 50 patients would yield a 95% confidence interval for the proportion of response with a half-width of approximately 15%.

The sample size was increased to 55 patients to account for a potential 10% drop-out rate, thus yielding a total planned sample size of 55 patients.

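### SAP 7.2.2.3 fixes a Gaussian CI, with no fallback, for by-visit response rates: with 4 or fewer responders or non-responders a limit leaves 0–100%, and at 0/55 or 55/55 the interval is only ±0.9 points

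*SAP*

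**What the plan says.** SAP 7.2.2.3 summarises Complete TMA Response by visit, "along with a 2-sided 95% CI for each postbaseline time point". The four component rates are handled the same way: "This summary will be accompanied by a similar presentation for the components of complete TMA response". These are platelet normalization, LDH normalization, both together, and the 25% creatinine improvement. One method is named for all of them: "The CIs will be based on the asymptotic Gaussian approximation method with a continuity correction". Similar summaries follow without the confirmation requirement and for the definition modified for patients on dialysis at baseline. For the per protocol set, "The tabular summary of complete TMA response over time will also be performed on the PPS".

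The section has no truncation rule, no small-count rule and no switch to another method. Protocol 15.8.2.3 asks only for a 2-sided 95% CI and names no method.

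Elsewhere the SAP uses exact limits for proportions over time. For dialysis status (7.2.2.1): "The CI will be based on exact confidence limits using the Clopper-Pearson method". For CKD stage (7.2.2.5): "The CIs will be based on exact confidence limits using the Clopper-Pearson method". Section 7.2.1.2 also uses Clopper-Pearson for the subgroup analyses of the primary endpoint, because the subgroups may be small.

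**The concern.** The Gaussian interval takes its width from the estimated standard error, which shrinks to zero as the observed proportion approaches 0% or 100%. That is where a small sample leaves the most relative uncertainty, and by-visit tables are likely to reach such values. The composite needs platelets, LDH and creatinine to respond together, so few patients may qualify at Day 8 or Day 15. Later, almost every patient may have normalised on a single hematologic component.

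SAP 7.2.1.4 describes an estimation study with no formal tests, so the interval is the stated measure of uncertainty. SAP 7.2.1 says results will be read in the context of eculizumab studies. A table giving ±1 point from about 55 patients, a negative limit or a limit above 100% would misstate what the data show.

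**Working it through.** **Inputs.** Sample size from SAP 9.3: "Approximately 55 patients will be enrolled in this study in order to yield at least 50 evaluable patients by Day 183", so n = 55 and n = 50. Planning rate 65% and stated half-width of about 15 points, also SAP 9.3. Two-sided 95%, so z = 1.96.

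**Formula.** With x responders and p = x/n, the limits are p ± [z·√(p(1−p)/n) + 1/(2n)], not truncated. The comparison is Clopper-Pearson, from beta quantiles.

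**The plan's own figure.** At p = 0.65, n = 50: 1.96·√(0.65·0.35/50) = 13.2 points, plus 1/(2·50) = 1.0 point, gives 14.2 points. This agrees with the stated figure after rounding. The formula behaves well there: exact coverage at a true 65% is 94.5% (n = 50) and 96.4% (n = 55).

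**Extreme counts, n = 55.**

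| Responders | Planned interval (%) | Exact interval (%) |
|---|---|---|
| 0 | −0.9 to 0.9 | 0 to 6.5 |
| 1 | −2.6 to 6.3 | 0.05 to 9.7 |
| 4 | −0.5 to 15.0 | 2.0 to 17.6 |
| 5 | 0.6 to 17.6 | 3.0 to 20.0 |
| 36 | 52.0 to 78.9 | 51.4 to 77.8 |
| 51 | 85.0 to 100.5 | 82.4 to 98.0 |
| 55 | 99.1 to 100.9 | 93.5 to 100 |

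At x = 0 the square root is zero and the half-width is 1/(2·55) = 0.91 points. The upper limit of 0.9% is about one seventh of the exact 6.5%. At n = 50 the half-width is 1.0 point against an exact upper limit of 7.1%; at n = 30 it is 1.7 points against 11.6%.

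**Where the limits become impossible.** At n = 55 the lower limit is −0.50% at x = 4 and +0.58% at x = 5. At n = 50 it is −0.52% and +0.68%. The cutoff of 4 was the same at every n checked from 20 to 60; it is lower below n = 20. Counts near n mirror this at the upper limit.

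**Coverage.** At n = 55 the interval for 0 responders stops at 0.91%, so any larger true rate is missed whenever nobody responds. At a true 2% that happens with probability 0.98^55 = 32.9%, leaving 67.1% coverage. At a true 1% it is 0.99^55 = 57.5%, leaving 42.5%. Full binomial sums give:

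| True rate (or its mirror) | n = 55 | n = 50 |
|---|---|---|
| 1% | 42.5% | 100% |
| 2% | 67.1% | 63.6% |
| 3% | 81.1% | 78.1% |
| 4% | 89.3% | 86.9% |
| 5% | 93.9% | 92.2% |

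The 100% at n = 50 arises because the interval for 0 responders reaches just to 1.0%; at a true 1.5% coverage is 53.0%. On a grid of true rates up to 50% in steps of 0.01 point, coverage is below 90% at 0.91–4.13% and 6.26–6.98% (n = 55, plus one isolated point at 9.5%), and at 1.01–4.53% and 6.89–7.65% (n = 50). The minimum is 39.5% and 39.8%. Clopper-Pearson never falls below 95.0% and 95.1% on the same grid.

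**The case against.** The strongest reply is that the harm depends on counts the documents do not give. The only planning rate is 65%, where the method works, and on the n = 55 grid coverage falls below 90% over only about 8% of true rates: (3.22 + 0.72)/50. Early component rates need not be near zero. Protocol 8 requires only "A minimum of 30 patients who meet all laboratory criteria for TMA" on Day 1, out of about 55, so some patients may start with normal platelets or LDH. A composite planned at 65% is also unlikely to approach 100%. This stands as a limit on how often the problem would show. It does not remove the early visits for the composite or the late visits for a single component.

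Second, software might clip the limits to 0–100%. The SAP neither requires nor excludes this. Clipping would hide the impossible values, but 0/55 would still read 0% to 0.9% and the undercoverage would remain.

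Third, the Gaussian method matches the primary analysis of the same endpoint, and exact limits elsewhere may have been chosen for small denominators. That explains part of 7.2.2.1 and 7.2.2.5. However, the overall dialysis summary and the CKD category for an unchanged stage are not restricted to a baseline subset. The SAP also already reports the primary endpoint with two methods, Gaussian overall and exact in subgroups.

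Finally, these are secondary descriptive tables with the counts printed beside each interval, and no decision rule uses them. That limits the seriousness but does not make the intervals right.

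**Conclusion.** The concern holds. As written, the by-visit intervals in SAP 7.2.2.3 fail at extreme counts. At the planned sample size a limit is impossible when 4 or fewer patients respond or fail, and at 0% or 100% the interval is ±0.9 points (n = 55) or ±1.0 point (n = 50), where exact limits allow 6.5 to 7.1 points. Coverage drops to about 40% at worst.

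This assumes untruncated limits, per-visit denominators near 50 to 55, and that some visits produce such counts. The last is plausible but cannot be established from the documents. The point should be corrected but is not critical: it concerns secondary by-visit tables, and the primary proportion and its interval are not in question.

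**What to change.** In SAP 7.2.2.3 replace the sentence on the CI method with the wording already used in 7.2.2.5: "The CIs will be based on exact confidence limits using the Clopper-Pearson method". State that it applies to every by-visit proportion in the section: Complete TMA Response, its components, the unconfirmed version, the dialysis-modified version and the per protocol repeat. The primary interval in 7.2.1 can stay as planned.

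The cost is one sentence and one option in existing code. Overall Complete TMA Response would then carry a Gaussian interval in the primary analysis and exact intervals by visit. The practical difference in mid-range is small: at 36/55 the width is 26.3 points instead of 26.9. Near the extremes the intervals widen, from 1.8 to 6.5 points at 0/55, which is the uncertainty the present formula leaves out.
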